## LIST OF ABBREVIATIONS AND DEFINITIONS OF TERMS

---

| Term   | Definition  |
|--------|---|
| AE     | adverse event   |
| ATC    | Anatomical Therapeutic Chemical                             |
| ATP    | Adenosine Triphosphate                                      |
| bpm    | Beats per minute  |
| C2     | Concentration of cough challenge inducing at least 2 coughs |
| C5     | Concentration of cough challenge inducing at least 5 coughs |
| CI     | Confidence Interval   |
| ECG    | Electrocardiogram   |
| eCRF   | electronic case report form                                 |
| EDC    | electronic data capture                                     |
| GCP    | Good Clinical Practice                                      |
| LN     | Natural log   |
| MedDRA | Medical Dictionary for regulatory Activities                |
| PCI    | Potentially Clinically Important                            |
| PPS    | Per protocol set  |
| SAE    | serious adverse event                                       |
| SAP    | statistical analysis plan                                   |
| SPSS   | Statistical package for social sciences                     |
| TEAE   | treatment-emergent adverse event                            |
| URTI   | upper respiratory tract infection                           |
| UTC    | urge-to-cough   |
| VAS    | Visual analogue scale                                       |
| WHO    | World Health Organization                                   |

---

---

## 1.0 INTRODUCTION

This statistical analysis plan (SAP) outlines the data and procedures used for assessing the safety and tolerability of ambroxol from Protocol IIT15419: A single-centre, open-label, exploratory study of the effect of 20 mg ambroxol hydrochloride on cough reflex sensitivity in patients with acute cough.

## 2.0 STUDY OBJECTIVE

### 2.1 Primary Objectives

The primary objective is to:

- To assess the effect of a single doses of 20 mg ambroxol hydrochloride on cough reflex sensitivity to citric acid, capsaicin, adenosine triphosphate (ATP) and distilled water in patients with acute cough related to upper respiratory tract infection.

### 2.2 Secondary Objectives

- To determine the effect of single dose of 20 mg ambroxol hydrochloride on cough severity visual analogue scale (VAS) and urge-to-cough VAS in subjects with acute cough related to upper respiratory tract viral infection.
- To evaluate changes in cough reflex sensitivity during acute cough associated with URTI in relation to the healthy (post-recovery) state.
- To evaluate changes in cough severity and urge to cough VAS during acute cough in relation to the post recovery state.
- To assess the safety and tolerability of ambroxol

## 3.0 STUDY DESIGN AND PROCEDURES

This was an open label, single centre exploratory study in patients with acute cough related to respiratory tract infection.

There was a Screening/Baseline and combined Treatment visit. Subjects return approximately 1-4 weeks after their treatment once all symptoms had subsided and the subject was no longer suffering from URTI, for a Follow-up Visit.

14 subjects with acute cough in relation to a URTI and who meet all entry criteria were be assigned to:

**Treatment** p.o 20mg ambroxol lozenge  
(Lysopain Ambr MintM)

At the Screening Visit/Baseline Visits and during Treatment phase, cough sensitivity (Section 5.1) was measured by standard clinical methodology incorporating four cough challenges (capsaicin, ATP, citric acid and distilled water).

Refer to the Schedule of Assessments and Procedures located at the end of the SAP (Appendix A) for additional details. The study includes the following study periods and scheduled visits:

### **Screening**

The purpose of the Screening/baseline 1a visit, was to ensure that each subject met all the specified inclusion and none of the exclusion criteria.

### **Baseline Visit 1a**

Subjects who satisfied all entry criteria at Screening continued in to the Baseline cough 1a visit for cough challenge assessments.

### **Treatment Phase 1b**

Subjects who satisfied all entry criteria at baseline were then administered 20 mg ambroxol in the form of a lozenge, which was sucked until fully dissolved in the mouth.

The treatment was administered in the afternoon of the same visit day as the screening/baseline assessments.

The series of abbreviated cough challenges were conducted at 30 min and 90 min post dose.

### **Telephone Contact**

Patients were contacted by phone once/week to establish if all symptoms associated with URTI has abated. Once this had been confirmed the patients were booked in for a follow-up visit.

### **Follow-Up/Early Withdrawal Visit**

Subjects returned within 4 weeks after treatment for a Follow-Up Visit once symptoms of URTI had abated. A series of full cough challenges were performed at this visit to determine reduction in cough hypersensitivity.

### **3.1 Treatment Assignment**

All subjects meeting inclusion/exclusion criteria were assigned to the 20mg ambroxol lozenge (Lysopain Ambr MintM).

### **4.0 INTERIM ANALYSES**

No interim analysis was planned for this study.

### **5.0 EFFICACY ASSESSMENTS**

#### **5.1 Cough Reflex Sensitivity**

Cough reflex sensitivity is measured by standard clinical methodology incorporating capsaicin, ATP, citric acid and distilled water cough challenges. The endpoints measured in cough challenge testing are concentrations of the challenge agents inducing 2 or more ( $C_2$ ) and 5 or more coughs ( $C_5$ ). In the case of distilled water the number of coughs generated in 1 minutes exposure will be recorded.

Cough challenges were carried out in accordance with the Study Site Standard Operating Procedures. Concentration range is pre-defined for each cough challenge agent and listed as below:

Distilled Water % Distilled Saline Control: 20%, 40%, 60%, 80%, 100%

Citric Acid Saline: 1 mM, 3 mM, 10 mM, 30 mM, 100 mM, 300 mM, 1M, 3M

Capsaicin Saline: 0.3  $\mu$ M, 1  $\mu$ M, 3  $\mu$ M, 10  $\mu$ M, 30  $\mu$ M, 100  $\mu$ M, 300  $\mu$ M, 1000  $\mu$ M

ATP Saline: 0.1 mM, 0.3 mM, 1 mM, 3 mM, 10 mM, 30 mM, 100 mM, 300 mM

Capsaicin, Citric Acid, ATP, and Distilled Water cough challenges will be administered 10 minutes apart and in a specific order for each subject (citric acid, capsaicin, ATP and distilled water) to determine  $C_2$  and  $C_5$ . Cough reflex sensitivity testing will be conducted at Baseline, at treatment phase 1b, 30 min and 90 min post dosing and at the Follow-up visit.

## **5.2 Cough Frequency and Cough Severity**

### **5.2.1 Visual Analogue Scales**

Subjects were to complete two visual analogue scales (VAS) at screening, prior to dosing and at 30 min and 90 min post dose at treatment phase 1b. A further two VAS forms were recorded at the follow-up visit.

The first scale was a 100mm horizontal line representing a scale of cough severity from ‘No Cough’ at the left hand end of the line up to ‘Worst Cough’ at the right hand end. The participant was to be instructed to draw a single vertical line on the scale to indicate how severe they felt their cough was during the previous 30 and 90 min at Treatment phase 1b and over last 24hrs at baseline and follow-up.

A second 100 mm scale was used to record the severity of their urge to cough but marked at the extremes as ‘No urge-to-cough’ and ‘Worst urge-to-cough’. Again, the participant was instructed to draw a single vertical line on the scale to indicate how severe their urge to cough was during the previous 30 and 90 min at Treatment phase 1b and over last 24hrs at baseline and follow-up.

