### **5.3.2 Secondary Efficacy Endpoints**

Secondary endpoints that will be assessed include:

- Urge to cough (UTC) 30 min and 90 min post last cough challenge
- Cough severity Visual Analog Scale (VAS) 30 and 90 min post last challenge.
- To evaluate changes in cough reflex sensitivity during acute cough associated with URTI in relation to the healthy (post-recovery) state

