## **9.0 GENERAL STATISTICAL CONSIDERATIONS**

Cough challenge analyses, cough frequency and urge to cough analysis and recovery will be conducted using SPSS (version.22) and Excel.

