### **10.5.2 Secondary Endpoints**

The secondary endpoints for subjects will be analysed using a one way ANOVA for repeated measures model with Bonferroni corrected post hoc measurements. The ANOVA model will use all available data at 30 min and 90 min post dose with Vas Scores as dependent variables and time points as independent variable.

The mean VAS scores with the associated standard errors will be displayed, Estimated differences from baseline along with corresponding 95% CIs and p-values will also be presented.

To analyse post-recovery change in C2 and C5, a mixed linear model will be performed with change from recovery in C2 and C5 concentration modeled as the response.

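### Post-dose VAS changes are tested against a baseline with a different recall window, while the recall-matched acute versus post-recovery VAS objective has no listed endpoint and no planned estimate

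*SAP*

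**What the plan says.** Section 5.2.1 describes two 100 mm scales, cough severity and urge to cough. For both, the period to be rated is "during the previous 30 and 90 min at Treatment phase 1b and over last 24hrs at baseline and follow-up". Appendix A shows one VAS mark in the Screening/Baseline column, one in the treatment column (note b: 30 and 90 min after treatment) and one at follow-up.

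Section 10.5.2 analyses VAS by one-way repeated-measures ANOVA with Bonferroni post hoc comparisons: "The ANOVA model will use all available data at 30 min and 90 min post dose with Vas Scores as dependent variables". The output is described as "The mean VAS scores with the associated standard errors will be displayed, Estimated differences from baseline along with corresponding 95% CIs and p-values".

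On recovery, section 2.2 has the objective "To evaluate changes in cough severity and urge to cough VAS during acute cough in relation to the post recovery state". Section 5.3.2 lists VAS only at 30 and 90 min. Its one recovery item is "To evaluate changes in cough reflex sensitivity during acute cough associated with URTI in relation to the healthy (post-recovery) state". For recovery, section 10.5.2 says "a mixed linear model will be performed with change from recovery in" C2 and C5. Section 9.0 mentions recovery only when naming software: "Cough challenge analyses, cough frequency and urge to cough analysis and recovery will be conducted using SPSS (version.22) and Excel". Section 9.1 promises efficacy tables by time point.

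On timing, section 5.3.2 gives "Cough severity Visual Analog Scale (VAS) 30 and 90 min post last challenge", and dates urge to cough from the last challenge as well. Sections 5.2.1 and 10.5.2 and Appendix A note b count from dosing.

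**The concern.** A difference from baseline is interpretable when the same question is asked on both occasions. Here the baseline rating summarises a day and the post-dose ratings summarise half an hour or an hour and a half. A subject whose cough is unchanged could still mark the line in a different place because the period has changed. With one open-label arm, the subject's own baseline is the only comparator, so no control group subtracts that effect. A p-value on the difference could reflect dosing, the change of question, or both. The Bonferroni correction deals with the number of comparisons, not with this.

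The comparison that is free of this problem, the 24-h rating when ill against the 24-h rating after recovery, is a stated objective with data collected, yet the SAP plans no estimate for it. The plan therefore gives inference to the mismatched comparison and none to the matched one.

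**Working it through.** **Step 1: recall windows.** I read 5.2.1 as a 30-min window for the 30-min rating and a 90-min window for the 90-min rating.

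| Contrast | Windows (min) | Ratio |
|---|---|---|
| 30 min vs baseline | 30 vs 1440 | 1440/30 = 48 |
| 90 min vs baseline | 90 vs 1440 | 1440/90 = 16 |
| 90 min vs 30 min | 90 vs 30 | 90/30 = 3 |
| Follow-up vs baseline | 1440 vs 1440 | 1 |

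These are ratios of question length, not of bias. None of the three contrasts available to the VAS model is matched. The only matched one lies outside it.

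**Step 2: is there a matched pre-dose rating?** Section 5.2.1 assigns 24 h to baseline, and the treatment-column VAS in Appendix A is at 30 and 90 min only. The SAP gives no pre-dose rating a short window.

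**Step 3: is the recovery VAS contrast covered elsewhere?**
- 2.2: objective stated for VAS, next to a parallel one for cough reflex sensitivity.
- 5.2.1 and Appendix A: follow-up VAS collected.
- 5.3.2: recovery endpoint for cough reflex sensitivity only.
- 10.5.2: recovery model for C2 and C5 only.
- 9.0: software only.
- 9.1: tables by time point, which describe each visit but do not estimate a within-subject difference.

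Of the two parallel objectives, one is carried through to an endpoint and a model and the other is not.

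**Step 4: brief illustration.** The SAP gives no VAS standard deviation or effect size, so there is no figure of its own to reproduce. The shifts and SDs below are assumptions; only n = 14 comes from the SAP. I use a paired t-test (df = 13) as an approximation to the post hoc contrast. The SAP does not fix the number of Bonferroni comparisons, so I show two (0.05/2 = 0.025) and three (0.05/3 = 0.0167), taking 0.05 as the overall level. The noncentrality is shift × √14 / SD; for 10 mm and SD 20 mm it is 0.5 × 3.742 = 1.87. Critical t is 2.533 (two comparisons) or 2.746 (three).

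Probability of a significant result with no true effect, SD 20 mm:

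| Shift from the question alone | Two comparisons | Three comparisons |
|---|---|---|
| 0 mm | 0.025 | 0.017 |
| 5 mm | 0.083 | 0.060 |
| 10 mm | 0.292 | 0.234 |

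For the 10 mm shift, moving the SD from 15 to 25 mm gives 0.505 to 0.188 (two) and 0.432 to 0.145 (three).

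The shift can also hide an effect. With an assumed true change of 15 mm, SD 20 mm and three comparisons, the chance of detection is 0.541 with no shift. It falls to 0.234 with an opposing 5 mm shift (net 10 mm) and to 0.060 with 10 mm (net 5 mm).

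**The case against.** *The bias is unquantified.* True. Nothing in the SAP gives its size or sign, and every probability above rests on assumed values. A reader might infer that the mismatch will produce a spurious benefit. The document does not support that: the shift could be zero, could mimic an effect or could mask one. What stands is that the planned p-value cannot be attributed to dosing.

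*The mismatch is in the data, so the SAP cannot repair it, and dropping p-values while keeping CIs changes little.* Largely right. A CI around a mismatched difference carries the same bias, and whether it excludes zero invites the same inference. Removing p-values is enough only if the SAP also says that the estimates and CIs are not treatment effects.

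*The sentence limiting the VAS model to 30- and 90-min data cannot be read strictly, because it would then exclude baseline too.* Fair, and the omission should not be argued from that sentence. It rests on 5.3.2, which lists no VAS recovery endpoint, and on the recovery model, which names only C2 and C5. The general opening of 10.5.2 refers to the secondary endpoints, so it does not bring in an endpoint that is not listed.

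*A pre-dose rating may exist.* The 5.2.1 wording on screening and pre-dose could be read as two occasions. The single Screening/Baseline mark in Appendix A makes that reading thin, and no short window is assigned either way. Nor would naming a particular VAS baseline conflict with 8.1, which allows stated exceptions.

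*Little is lost on recovery.* Follow-up is booked only after symptoms have abated, so a fall is partly built in, and 9.1 already gives descriptive tables. This limits what the contrast can show. It does not explain why a stated objective has no planned estimate.

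*The study is exploratory and VAS is secondary.* This lowers the weight, but the SAP still prespecifies p-values and calls its analyses a priori.

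**Conclusion.** The point holds on the text, at the level of a change that should be made. The post-dose VAS differences from baseline confound time point with recall window, and the single-arm design offers nothing to separate them. The recall-matched acute versus post-recovery VAS objective has no listed endpoint and no inferential analysis. The VAS time origin in 5.3.2 conflicts with 5.2.1, 10.5.2 and Appendix A note b.

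Three stronger readings are not supported. A reader might infer that the VAS results are biased in a known direction or by a known amount; the document gives no basis for either. A reader might infer that follow-up VAS goes wholly unreported; the tables under 9.1 would still describe it. A reader might also infer that the 90-min window necessarily takes in a challenge series; that depends on the unresolved time origin and on challenge durations the SAP does not give.

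The conclusion does not depend on the illustrative probabilities. The primary C2 and C5 analyses do not use the VAS and are not affected by this point.

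**What to change.** Amend the SAP before database lock. Under 9.1, an analysis not described in the SAP and performed after lock counts as post hoc and exploratory.

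1. In 10.5.2, report the 30- and 90-min VAS changes from the 24-h baseline as descriptive only, without p-values. State the recall mismatch beside them, and state that neither the estimates nor their CIs are to be read as a treatment effect. If a pre-dose rating with a matching recall window was recorded, this restriction need not apply to comparisons with that rating.
2. Add to 5.3.2 an endpoint, and to 10.5.2 a paired mean difference with 95% CI, for 24-h baseline versus 24-h follow-up on both VAS scores. Note that follow-up is booked only once symptoms have abated, so part of any fall is built in.
3. Reconcile the VAS time origin in 5.3.2 (last cough challenge) with 5.2.1, 10.5.2 and Appendix A note b (dosing).

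The cost is SAP wording and the loss of the post-dose VAS p-values. No new data are needed, the post-dose estimates and CIs are kept, and an objective already in 2.2 gains an endpoint and an estimate.

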## **5.3 Efficacy Endpoints**

### **5.3.1 Primary Efficacy Endpoints**

The co-primary endpoints are the average C2 and C5 across three time points (at baseline, 30 min, and 90 min post-dose) for capsaicin, ATP, citric acid and distilled water challenge: concentration inducing at least 2 coughs and at least 5 coughs. The primary endpoints include:

- Average C2 and C5 for capsaicin challenge
- Average C2 and C5 for ATP challenge
- Average C2 and C5 for citric acid challenge
- Average C2 and C5 for distilled water challenge

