## **8.0 DEFINITION OF VARIABLES**

### **8.1 Baseline**

Unless otherwise stated, baseline is defined as the last observation recorded on or prior to the first study treatment.

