### **10.5.1 Primary Endpoints**

Cough reflex sensitivity is measured by standard clinical methodology incorporating capsaicin, citric acid, ATP, and distilled water cough challenges. The standard end points measured in cough challenge testing are the concentrations of the challenge agents inducing 2 or more (C2) and 5 or more coughs (C5). In the case of distilled water the number of coughs generated in 30 seconds exposure will be recorded.

A natural log (LN) C2 and C5 is generally regarded as normally distributed within a population, so the treatment comparison will be performed using an ANOVA repeated measures model with Bonferroni corrected post hoc measurements. The ANOVA model will use all available data at 30 min and 90 min post dose with LN C2 and LNC5 as dependent variables and time points as independent variable.

The mean (in log scale) with the associated standard errors will be displayed which will be the average of C2 or C5 across three timepoints. Estimated differences from baseline along with corresponding 95% CIs and p-values will also be presented.

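### The primary analysis uses baseline in three incompatible ways, and as worded its ANOVA tests only 30 min against 90 min post-dose

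*SAP*

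**What the plan says.** Section 8.1 fixes the reference value: "baseline is defined as the last observation recorded on or prior to the first study treatment". The primary analysis then refers to baseline in three ways.

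- **As part of the endpoint.** Section 5.3.1: "The co-primary endpoints are the average C2 and C5 across three time points (at baseline, 30 min, and 90 min post-dose". The four bullets beneath it repeat the average for each challenge agent. Section 10.5.1 does the same for the displayed log-scale mean, "which will be the average of C2 or C5 across three timepoints".
- **Left out of the model data.** Section 10.5.1: "The ANOVA model will use all available data at 30 min and 90 min post dose", with "time points as independent variable". No baseline covariate and no change-from-baseline response is named. The method is an "ANOVA repeated measures model with Bonferroni corrected post hoc measurements".
- **As the comparator.** Section 10.5.1 closes: "Estimated differences from baseline along with corresponding 95% CIs and p-values will also be presented".

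Section 10.5.2 carries the same data sentence over to the visual analogue scales ("The ANOVA model will use all available data at 30 min and 90 min post dose with Vas Scores as dependent variables"), again next to promised differences from baseline.

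**The concern.** The primary objective (section 2.1) is the effect of a single dose on cough reflex sensitivity, and every subject receives that dose (section 3.1). The pre-dose value is the only untreated reference taken during the acute cough, so the way baseline enters the analysis decides whether the primary question is answered at all.

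An average that includes baseline is not a comparison: in one arm it has no comparator and no null value. A model holding only the two post-dose measurements cannot estimate a difference from baseline. Its time test asks whether sensitivity changed between 30 and 90 min, which concerns the persistence of an effect rather than its existence.

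Section 9.1 calls the described analyses a priori because they were defined before database lock. With three conflicting descriptions the primary analysis is not fixed in that sense. Someone would have to pick a reading with open-label data in hand.

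**Working it through.** **Inputs from the SAP.** 14 subjects in one arm (section 3.0); natural-log C2 and C5 as responses and time as the only factor (section 10.5.1). Section 9.3 gives no effect size, SD or power, so there is no planned figure to reproduce.

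**Assumptions.** Within-subject residual SD of 0.8 or 1.0 on the natural-log scale; two-sided alpha 0.05; complete data; equal variances and correlations over time. The shifts from baseline are illustrative: 3-fold (ln 3 = 1.099) and 0.55 (1.73-fold). Between-subject SD cancels.

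**1. The average.** Let d30 and d90 be the changes from baseline. The three-timepoint average is

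baseline + (0 + d30 + d90)/3.

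An equal shift d enters as 2d/3, so a doubling (0.693) appears as 0.462, added to a baseline level that the average alone cannot separate out.

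**2. The structure of the test.**

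| | As worded | Baseline added |
|---|---|---|
| Levels of time | 30, 90 min | baseline, 30, 90 min |
| F degrees of freedom | 1, 13 | 2, 26 |
| Possible pairs | 1 | 3 |
| Differences from baseline estimable | no | yes |

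With one pair, Bonferroni has nothing to correct.

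**3. Power of the time F-test.** For k levels with means μj,

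ncp = 14 × Σ(μj − mean μ)² / SD², with df k−1 and 13(k−1),

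and power comes from the noncentral F distribution.

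Example, equal 3-fold shift:
- As worded, the means are 1.099 and 1.099. The sum of squares is 0, ncp = 0, and rejection is 5% at any SD.
- With baseline, the means are 0, 1.099 and 1.099. The sum of squares is (2/3) × 1.099² = 0.805. At SD 0.8, ncp = 14 × 0.805/0.64 = 17.6; at SD 1.0, ncp = 11.3.

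| True change from baseline | As worded, SD 0.8 / 1.0 | Three levels, SD 0.8 / 1.0 |
|---|---|---|
| 3-fold at both times | 5% / 5% | 95% / 82% |
| 0.55 at both times | 5% / 5% | 41% / 28% |
| 3-fold, falling to 0.55 at 90 min | 39% / 27% | 88% / 69% |
| 3-fold, gone by 90 min | 92% / 77% | 95% / 82% |

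The literal test does worst when the change is sustained and approaches the three-level test only when the change has vanished by 90 min.

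**4. Power of the two contrasts with baseline.** The F-test figures are not the power of the individual comparisons. For a paired t-test of one post-dose time against baseline at 0.025 (0.05/2), the noncentrality is 1.099/(SD × √(2/14)) = 3.63 at SD 0.8 and 2.91 at SD 1.0. For an equal 3-fold shift, each contrast has power 85% / 65%, at least one succeeds in 95% / 81% of trials, and both succeed in 75% / 49%. If the change is gone by 90 min, at least one succeeds in 86% / 66%.

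**The case against.** The strongest reply is that the intended analysis can be inferred. The promised differences from baseline, the mention of three timepoints and the Bonferroni correction all point to a three-level time factor. Section 9.1 also says that efficacy tables are presented by time point, so the average could be read as the group mean at each of three times. On that reading only one data sentence, with its copy in 10.5.2, is faulty, and the 5% rejection rate describes an analysis nobody would run.

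The inference about intent is fair, and the figures should not be read as a forecast of what the trial will do. It does not settle the matter. An average across three timepoints, stated in the endpoint definition and again in the analysis section, is hard to read as three separate means. Even on the generous reading, the sentence naming the model data still omits baseline.

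A second reply also has substance: the F-test power overstates what the recommended contrasts deliver singly. When the change has gone by 90 min, the chance that at least one contrast succeeds (86% / 66%) is below that of the literal two-level test (92% / 77%). That is true, but in that case the literal test is detecting waning and still gives no estimate of change from baseline.

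Finally, this is an exploratory study with no power claim. That lowers the stakes of any single p-value but does not excuse a primary endpoint, model and output that disagree.

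**Conclusion.** The concern holds, and the text must be corrected before analysis. The endpoint, the model and the output in sections 5.3.1 and 10.5.1 describe three different analyses, and the model as written cannot produce the output promised in the same section. This conclusion needs no assumption. Nor does the 5% rejection rate for a change that is equal at 30 and 90 min: it holds at any SD and any effect size.

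The other power figures depend on the assumed SDs and shifts. Under them, the loss is total for a sustained change, large for a partly waning one, and small only for one that has gone by 90 min. A three-level factor was probably intended, so this is a defect of specification and not proof that the wrong test would be run.

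**What to change.** - **Section 5.3.1.** Define the co-primary endpoints as the change from pre-dose baseline in LN C2 and LN C5, at 30 min and at 90 min, for capsaicin, citric acid and ATP. Delete the three-timepoint average from the lead sentence and the four bullets. For distilled water, first settle whether the outcome is C2/C5 (5.3.1) or a cough count (5.1 and 10.5.1, which also disagree on 1 minute or 30 seconds of exposure), then use its change from baseline.
- **Section 10.5.1.** Replace the data sentence with one stating that the repeated-measures model uses baseline, 30 min and 90 min as three levels of time, and that the primary comparisons are 30 min versus baseline and 90 min versus baseline, Bonferroni corrected for those two. Say whether a positive conclusion needs one comparison or both. Show the mean at each time in place of the average. A mixed model with random subject is an option and would honour the intention to use all available data.
- **Section 10.5.2.** Correct the VAS data sentence in the same way. Note that the baseline VAS covers 24 hours and the post-dose VAS 30 or 90 min (section 5.2.1).
- **Reporting.** Describe the result as a pre-post change, not a controlled drug effect. There is no control arm. Appendix A lists full challenges 30 min apart at baseline but abbreviated ones 10 min apart after dosing, whereas section 5.1 gives 10 minutes without distinguishing visits; these passages must be reconciled.

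The cost is SAP wording: the lead sentence and bullets in 5.3.1, two sentences in 10.5.1, one in 10.5.2 and short notes on distilled water, the VAS and reporting. Baseline, 30 min and 90 min measurements are already scheduled, so no new data are needed.
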